5 STUDY EVALUATIONS AND MEASUREMENTS

5.1 Measurements

Procedures for PEEP and FiO2 Titration

Both groups will have their FiO2 titrated based on results of the PaO2 from an arterial blood gas, if available, or SpO2 values if no arterial blood gas is obtained. PEEP titration will vary by group as below.

Setting PEEP in Intervention Group

The waveforms of Paw, Pes, and Ptp will be visualized on the ventilator. Ptp is obtained from Paw – Pes. PEEP will be increased on the ventilator to achieve a Ptp between 0 and +2 cm H₂O (Optimal PEEP). Measurements will be obtained daily and adjustments to PEEP will occur daily. PEEP will be reduced below Optimal PEEP in the setting of hemodynamic compromise (requiring increasing vasoactive medications for blood pressure support).

Setting PEEP in Control Group

PEEP in the control group will be determined by High PEEP ARDSnet PEEP/FiO₂ table. Titration of PEEP will occur when clinically indicated by PaO₂ or SpO₂, and FiO₂. We chose the High PEEP table based on the clinical suspicion that obese patients may require higher PEEP levels on average than non-obese patients to balance the additional pressure of their chest wall. In addition, EPVent2, a study of esophageal balloon PEEP titration in patients with ARDS utilized the High PEEP table. Patients with moderate and severe ARDS benefit from higher levels of PEEP. (8)

Procedures for Assessment of Readiness for Extubation

Both groups will have a daily assessment of readiness for extubation performed by the Respiratory Therapist and bedside RN according to the standard clinical protocol. Criteria for both groups to undergo a spontaneous breathing trial (SBT) will be the following:

- 1) Not in prone position
- 2) No increased ICP
- 3) No active seizures
- 4) No alcohol withdrawal requiring escalating treatment
- 5) No active myocardial ischemia in discussion with nursing or physician
- 6) No unstable spine fractures
- 7) No free muscle flaps
- 8) FiO₂ ≤ 50% and SpO₂ ≥ 90%
- 9) Minute Ventilation < 15 L/min
- 10) Minimal vasopressors (norepinephrine < 5mcg/min or 0.05 mcg/kg/min, dopamine/dobutamine ≤ 5 mcg/kg/min)
- 11) HR < 140
- 12) RR ≤ 35
- 13) SBP > 90 and < 180

Failure of an SBT will be demonstrated if any of the following criteria are met:

- 1) SpO₂ < 90% sustained ≥ 5 minutes
- 2) Spontaneous VT ≤ 4ml/kg IBW – sustained ≥ 5 minutes
- 3) Respiratory Rate ≥ 35/min
- 4) Rapid Shallow Breathing Index >105
- 5) Other signs of respiratory distress (distress = 2 or more)
- 6) HR > 140
- 7) Marked accessory muscle use
- 8) Abdominal paradox (belly breathing)
- 9) Diaphoresis

Failure of an SBT will be determined by the bedside RT based on current policy (PolicyStat ID: 4745433). If a patient fails an SBT, they will be returned to their previous ventilator settings until the next daily assessment. If the patient tolerates a 30-minute SBT, they will be returned to their previous ventilator settings for 60 minutes, then extubated to an appropriate oxygen delivery device. Ventilator settings during the SBT and extubation procedures will vary between groups as below. Blinding of the respiratory therapist determining eligibility for SBT to treatment arm will not be possible because of the differences between SBT protocols. However, the study team will make no determinations of readiness for extubation. If a member of the study team is on service during the time of potential enrollment, these patients will be excluded to avoid bias.

SBT and Extubation Procedure for Intervention Group

Patients in the Intervention group will undergo an SBT regardless of their PEEP level. The PEEP that generates a Ptp of 0 will be considered their optimal PEEP, and this will not be lowered for the SBT. The Intervention Group SBT will consist of a trial of a pressure support of 5 cm H₂O and Optimal PEEP.

SBT and Extubation Procedure for Control Group

Patients in the Control group will undergo an SBT **when they reach a PEEP \leq 8 cm H₂O**. This is the current standard of care based on the SBT protocol at UNC Hospitals. SBT and extubation prior to meeting these criteria will be based on primary medical team's discretion and will be recorded for analysis and safety tracking.

Procedures for ventilator weaning after tracheostomy

Any patient who fails to be eligible for extubation or fails extubation will be eligible for tracheostomy per usual unit protocol. The study team will play no part in the decision to proceed with tracheostomy for ventilator weaning. After tracheostomy, it is routine practice to forego SBT and proceed with trials of liberation from the ventilator with oxygen delivered by an aerosol tracheostomy collar ("trach collar trials" or TCT). The same criteria are used to perform a TCT as an SBT above. The two groups will have different approaches to TCT.

TCT Procedure common to both groups

TCT will proceed for up to 12 hours as tolerated by the patient. Interval mechanical ventilation will be provided using a control mode of mechanical ventilation (typically PRVC with 6-8 ml/kg of IBW tidal volume). After 2 successful 12-hour TCT, a subsequent 24-hour TCT will be performed with no plan for interval mechanical ventilation. If the patient tolerates >48 hours of time free from mechanical ventilation, they will be considered liberated from mechanical ventilation. If they fail the 24-hour TCT, they will be placed back on mechanical ventilation and a subsequent 24-hour trial will be performed the following day. This pattern will continue until the patient is successfully liberated from mechanical ventilation.

TCT Procedure for Intervention Group

Based on the use of optimal PEEP in this group, and the experience in the previous study protocol (7), we will place patients in the Intervention group on TCT **ONLY** with a speaking valve. This simulates the normal process of utilizing the upper airway to maintain lung inflation that is performed automatically when a patient does not have an artificial airway.

TCT Procedure for Control Group

The control group will be placed on TCT with no requirement for speaking valve. They may utilize a speaking valve if tolerated and desired, but there is no requirement as there is in the Intervention group.

5.2 Other measurements

Variable	Source	How Measured	Baseline	Daily	Completion
Outcomes					
Ventilator free days at day 28 (Primary outcome)	EMR	Days alive and free of the ventilator			X
Reintubation	EMR	Intubated within 72 hours of extubation		X	X
ICU Length of Stay	EMR	Days			X
Hospital Length of Stay	EMR	Days			X
Tracheostomy	EMR	Y/N			X
Extubation prior to meeting established criteria	EMR	Y/N			X
Highest RASS	EMR	-5 to +4 (single highest value used)	X	X	
Lowest RASS	EMR	-5 to +4 (single lowest value used)	X	X	
Exposures					
Esophageal pressure (Pes)	Ventilator	cm H ₂ O	X	X	
Airway pressure (Paw)	Ventilator	cm H ₂ O	X	X	
Transpulmonary pressure (Ptp) (inspiratory and expiratory)	Ventilator	cm H ₂ O	X	X	
PEEP	Ventilator	cm H ₂ O	X	X	
Opioids	EMR	Continuous, bolus sch, bolus prn, oral sch, oral prn	X	X	
Propofol	EMR	Y/N	X	X	
Dexmedetomidine	EMR	Y/N	X	X	
Benzodiazepines	EMR	Continuous, bolus sch, bolus prn, oral sch, oral prn	X	X	
Antipsychotics	EMR	Sched, PRN	X	X	
Neuromuscular blockade	EMR	Y/N	X	X	
Corticosteroid use	EMR	Y/N	X	X	
Fluid Balance	EMR	Net fluid balance prior to extubation		X	
Safety Measures					
Vasopressor requirement	EMR	norepinephrine equivalents(9)	X	X	
Pneumothorax	EMR	Y/N	X	X	
Other Variables of Interest					
Age	EMR	Years	X		
Race/Ethnicity					
BMI	EMR	kg/m ²	X		
Partial Pressure of Oxygen (PaO ₂)	EMR	mmHg	X	X	
Oxygen Saturation (SpO ₂)	EMR	%	X	X	

PaO ₂ /FiO ₂ ratio	Calculated	Number	X	X	
SpO ₂ /FiO ₂ ratio	Calculated	Number	X	X	
Charlson Comorbidities	EMR	Y/N	X		
Waist circumference	EMR	cm	X		
CAM-ICU	EMR	Positive/Negative	X	X	
SOFA	EMR	Calculated	X		
COVID (y/n)	EMR	Y/N	X		

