3.3 Study Duration, Enrollment and Number of Participants

Enrollment will continue until 38 participants have been enrolled in each group (76 participants total). The medical ICU (MICU) admits approximately 150 per month, 40-50% of whom require mechanical ventilation. Based on a previous evaluation of lung protective ventilation in our hospital, approximately 45% of our patients requiring mechanical ventilation have a BMI ≥ 40 . Therefore, the MICU conservatively admits approximately 24 patients a month that meet inclusion criteria. Based on expected enrollment of at least 3-4 participants per month, the trial is expected to complete enrollment within 24 months. Each patient's participation will last 28 days or until death or hospital discharge.

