4.4 Participant Completion/ Withdrawal

Participants will complete the study at the time of death or the conclusion of 28 days, whichever occurs first.

Early completion of the trial for each participant will occur if any of the following outcomes are met:

- a. Patient or family withdraw consent for the study
- b. The clinical team feels that the patient no longer meets appropriateness for the study
- c. Patient develops an adverse effect felt possibly related to the intervention (refractory hypotension, nasopharyngeal bleeding, pneumothorax, etc)

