6.2 Statistical Methods

All continuous variables (see 5.2) will be described using mean and standard deviation, with associated 95% confidence intervals, or median with interquartile range as appropriate based on normality of distribution. All categorical variables will be described with frequency and percentage.

To determine if the optimal PEEP has an effect on the duration of mechanical ventilation compared to usual PEEP, the primary outcome will be analyzed with a 2-sided independent t-test. As secondary analysis, the associations between the primary outcome and exposures and demographic variables will be further analyzed using linear regression models.

The impact of optimal PEEP vs standardized PEEP titration will be assessed on all other variables with independent t-tests or chi-square tests as appropriate. All secondary outcomes, as described in 5.2, will be further analyzed with either linear regression models or logistic models, using demographic and exposure variables as predictors.

All tests will be 2-sided, and p-values < 0.05 will be considered significant. Tests with p-values above 0.05 will be considered inconclusive. Missing values will be ignored.

No interim analyses for efficacy or futility are planned, but interim analyses will be conducted for safety.

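### ICU and hospital length of stay are tested with no rule for patients who die, and mortality by arm is not a listed outcome, so early deaths can pass for short stays

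*Combined protocol and SAP*

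**What the plan says.** The outcomes block of the table in section 5.2 contains "ICU Length of Stay" and "Hospital Length of Stay". Both are in days, taken from the medical record and recorded at completion. The table has no mortality row, either among outcomes or among safety measures.

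Section 6.2 states that the effect of the PEEP strategy "will be assessed on all other variables with independent t-tests or chi-square tests as appropriate", and that secondary outcomes "will be further analyzed with either linear regression models or logistic models". For a variable in days this means a t-test followed by linear regression. The same section sets the threshold ("All tests will be 2-sided, and p-values < 0.05 will be considered significant") and the missing-data rule ("Missing values will be ignored").

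On the end of follow-up, section 4.4 says "Participants will complete the study at the time of death or the conclusion of 28 days, whichever occurs first". Section 3.3 says that each patient's "participation will last 28 days or until death or hospital discharge".

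Death appears in three other places:
- The primary outcome in section 6.1 counts only days on which the patient is alive and off the ventilator.
- Section 7.3 suspends the study for DSMB review if 8 of the first 10 patients die or, beyond 10 enrolled, 60% of those enrolled.
- The adverse-event grades in section 7.2 run to grade 5, but only for hypotension, pneumothorax and epistaxis.

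The between-group safety review in the synopsis names hypotension requiring vasopressors and pneumothorax, not death.

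**The concern.** A short stay is a good result only if the patient left alive. The plan does not separate leaving alive from dying, and the two natural readings of its silence both give a comparison that is hard to interpret.

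- **Death ends the stay.** Stay is recorded at completion and death is a completion event, so a patient who dies on day 5 would enter the t-test with a 5-day stay. The arm with more early deaths then gains an apparent advantage.
- **Deaths are treated as missing.** The section 6.2 rule would drop them. What remains is a comparison of survivors, a group defined by something that happened after randomisation.

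A by-arm mortality comparison would let a reader see which explanation applies, but none is planned. The DSMB trigger uses the share of all enrolled subjects, so it cannot show an imbalance between arms. At stake is whether a reported reduction in stay can be read as benefit.

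**Working it through.** **The plan's own figure.** The plan gives no figure for length of stay. The illustration uses its 38 per arm, which reproduces. With SD 2.9, two-sided alpha 0.05 and 80% power, a t-test needs 15.7 (so 16) per group for a 3-day difference and 34 for a 2-day difference. Then 68 / 0.90 = 75.6, so 76, or 38 per arm. Nothing in this point changes that number.

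**Assumed inputs (none are in the documents).** Mean stay is 12–18 days in survivors (L_s) and 4–8 days in patients who die (L_d). Mortality is 20% in one arm and 30% or 40% in the other. Survivors' stay is the same in both arms, so the true effect on it is nil.

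**Reading 1: death ends the stay.**

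Mean stay in an arm = (1 − m) × L_s + m × L_d

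Difference, higher-mortality arm minus the other = (m_high − m_low) × (L_d − L_s)

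| Mortality | Smallest (L_s 12, L_d 8) | Middle (L_s 15, L_d 6) | Largest (L_s 18, L_d 4) |
|---|---|---|---|
| 20% vs 30% | 0.10 × (−4) = −0.4 days | 0.10 × (−9) = −0.9 days | 0.10 × (−14) = −1.4 days |
| 20% vs 40% | 0.20 × (−4) = −0.8 days | 0.20 × (−9) = −1.8 days | 0.20 × (−14) = −2.8 days |

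The sign depends on deaths coming early. With L_d = L_s = 15 the difference is zero. With L_d = 20 and L_s = 15 it reverses: 0.10 × 5 = +0.5 days and 0.20 × 5 = +1.0 day.

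**How often the planned test would be misled.** This was simulated for the middle case: 38 per arm, gamma-distributed stays with an assumed coefficient of variation of 0.6, 20,000 trials for the t-test and 4,000 for a rank test that places deaths worst. The figures are the proportion of trials significantly favouring the higher-mortality arm (nominal 2.5%).

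| Mortality | Planned t-test | Rank test, death worst |
|---|---|---|
| 20% vs 20% | 2.6% | 2.4% |
| 20% vs 30% | 6.8% | 0.3% |
| 20% vs 40% | 14.2% | about 0% |

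With late deaths (20 days vs 15) the t-test figures are 1.5% at 20% vs 30% and 0.8% at 20% vs 40%, both below nominal.

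**Reading 2: deaths dropped.** At 20% vs 40% mortality, 38 × 0.80 = 30.4 and 38 × 0.60 = 22.8 patients are expected to remain. The bias has no fixed sign or size. It depends on how the extra deaths in one arm differ from the survivors, which the planned data cannot settle.

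**What the primary outcome would show.** Take the plan's 21 VFD (section 6.3) as the survivors' mean in both arms, and score deaths as 0. The zero is an assumption, since section 6.1 does not state it. Mean VFD is then 0.80 × 21 = 16.8 at 20% mortality, 0.70 × 21 = 14.7 at 30% and 0.60 × 21 = 12.6 at 40%. VFD moves against the higher-mortality arm by 2.1 and 4.2 days while mean stay moves in its favour.

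**The case against.** The strongest reply is that the primary outcome already guards against the error. That is largely right. A reader might infer that nothing in the planned comparisons would reveal excess deaths, and the documents do not support this: VFD counts days alive, and in the illustration it moves against the higher-mortality arm by more than stay moves in its favour. What stands is narrower. VFD mixes death with ventilator time and cannot say which produced the difference, so stay and VFD would disagree without a listed result to explain why.

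Other stronger readings also go too far:
- **That the plan scores death as an ordinary discharge.** It does not say so. This is the default that follows from having no rule, and the missing-data rule allows another reading.
- **That stays are cut off at day 28.** Sections 3.3 and 4.4 end participation by then, but stay comes from the medical record and no text says that it is truncated. The point is open.
- **That a false benefit is likely.** The size rests on assumed inputs and on deaths coming early. The exclusion of patients not expected to survive 48 hours removes some of the earliest deaths.
- **That the primary analysis is at fault.** Only secondary outcomes are directly affected.

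It is also fair to say that raw length of stay is a legitimate measure of resource use. It can be kept for that purpose, but its arm difference should not be tested as evidence of patient benefit.

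**Conclusion.** The point holds as a gap in the secondary analyses. The plan tests length of stay with no rule for patients who die, and it lists no by-arm mortality result that would let a reader interpret the test. Under the assumptions above, the apparent shortening in the higher-mortality arm is 0.4–1.4 days at 20% vs 30% mortality and 0.8–2.8 days at 20% vs 40%. In the middle case, false significance in that arm's favour rises from about 2.5% to about 7% and 14%. These figures illustrate the mechanism and do not predict the trial's result. They fall to no bias if patients who die stay as long as survivors, and change sign if they stay longer. Severity is minor to moderate.

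**What to change.** 1. Add 28-day mortality by arm to the table in section 5.2, and report it beside VFD and the stay outcomes.
2. In section 6.2, replace the t-test on raw stay with one pre-specified method. One option is ICU-free and hospital-free days to day 28, with death scored 0, compared by a rank test. The other is time to discharge alive, with death as a competing event.
3. Keep raw length of stay as a description by arm and survival status, with no formal test. State whether it is counted beyond day 28.

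**Cost.** This is a change of wording plus routine analysis, with no extra patients. Vital status to day 28 is already needed for VFD. Section 3.3 allows participation to end at hospital discharge, so the plan should confirm that vital status is obtained for patients discharged before day 28. The downside is that raw length of stay is no longer formally tested.

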6 STATISTICAL CONSIDERATION

6.1 Primary Endpoint

The primary outcome is the number of ventilator-free days (VFD), defined as the number of days alive and ventilator-free by day 28. The assessment of the primary outcome will be conducted by a study team member after subject completion in the study. In order to minimize potential bias, this team member will be blinded to treatment arm assignment.

6.2 Statistical Methods

All continuous variables (see 5.2) will be described using mean and standard deviation, with associated 95% confidence intervals, or median with interquartile range as appropriate based on normality of distribution. All categorical variables will be described with frequency and percentage.

To determine if the optimal PEEP has an effect on the duration of mechanical ventilation compared to usual PEEP, the primary outcome will be analyzed with a 2-sided independent t-test. As secondary analysis, the associations between the primary outcome and exposures and demographic variables will be further analyzed using linear regression models.

The impact of optimal PEEP vs standardized PEEP titration will be assessed on all other variables with independent t-tests or chi-square tests as appropriate. All secondary outcomes, as described in 5.2, will be further analyzed with either linear regression models or logistic models, using demographic and exposure variables as predictors.

All tests will be 2-sided, and p-values < 0.05 will be considered significant. Tests with p-values above 0.05 will be considered inconclusive. Missing values will be ignored.

No interim analyses for efficacy or futility are planned, but interim analyses will be conducted for safety.

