Safety Evaluations	Periodic review will be performed by the NC TraCS DSMB. They will review aggregate safety data after 25, 50, and 75% enrollment to ensure there are not safety differences between the groups in hypotension requiring vasopressors and development of pneumothorax. All patients will have

continuous monitoring of HR, BP, and oxygenation per ICU protocol to monitor patient safety.

Statistical And Analytic Plan

This is a randomized, controlled trial to evaluate the effect of using Optimal PEEP based on an esophageal balloon measurement on duration of mechanical ventilation. We hypothesize that using Ptp to identify optimal PEEP will reduce time on the ventilator and therefore increase the ventilator free days at day 28. The primary outcome is the number of ventilator-free days, defined as the number of days alive and ventilator-free by day 28. Differences between the two groups in the primary outcome will be analyzed using independent t-tests and a linear regression model adjusting for BMI, abdominal girth, and Ptp.

DATA AND SAFETY MONITORING PLAN

The PI will be responsible for maintaining patient data and ensuring accuracy of the data collected. All patient data will be collected using REDCap through the NC TraCS system. REDCap allows for immediate data validation and range setting to reduce the likelihood of erroneous data entry. Data created for analysis will be de-identified and secured on a password protected UNC School of Medicine network hard drive. All investigators will be trained on completing the electronic case report form.

Patient safety will be monitored with continuous cardiovascular monitoring by the critical care team. Subject stopping rules will be in place to end the study intervention, including refractory hypotension, development of pneumothorax, or changes in oxygenation or hemodynamics that the primary team feels may be related to changes in PEEP.

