2.1 Primary Objective

To determine if titration of PEEP to Optimal PEEP results in a reduction of the duration of mechanical ventilation in obese adults in a medical ICU.

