6.3 Sample Size and Power

We utilized preliminary data from earlier studies of mechanical ventilation in the obese to establish a baseline. With a mean duration of mechanical ventilation of 7 days with a standard deviation of 2.9 days, we expect the control group to have 21 ventilator free days. We estimate that we could reasonably see an effect in the intervention group that reduces the duration of mechanical ventilation by 3 days. With a power of 80% and alpha=0.05, we would need 16 patients per group, for a total of 32 patients. Would the effect be only a reduction of mechanical ventilation by 2 days, we would need 34 patients in each group for a total of 68 patients. Because the population in our study would be expected to have a lower mean duration of mechanical

ventilation, we anticipate we may find a smaller effect size. Including a possible 10% dropout, we will target a sample size of 76 (38 per group) to safely achieve our goals.

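### The planned test of ventilator-free days cannot separate an effect on ventilation duration from an effect on survival, yet the objective and section 6.2 are worded as duration

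*Combined protocol and SAP*

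**What the plan says.** Section 2.1 gives the objective as "To determine if titration of PEEP to Optimal PEEP results in a reduction of the duration of mechanical ventilation". Section 6.2 carries that target into the analysis: "To determine if the optimal PEEP has an effect on the duration of mechanical ventilation compared to usual PEEP, the primary outcome will be analyzed" by a two-sided t-test. The outcome tested is VFD, "defined as the number of days alive and ventilator-free by day 28" (6.1), listed in the 5.2 table as "Days alive and free of the ventilator". The synopsis (Statistical And Analytic Plan) links the two by hypothesising that the intervention "will reduce time on the ventilator and therefore increase the ventilator free days at day 28", without mentioning death.

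The other entries in the Outcomes block of 5.2 are reintubation, ICU and hospital stay, tracheostomy, extubation before criteria were met, and RASS. No row in any block of 5.2 is for death, days ventilated or time to liberation. Section 6.2 draws its further analyses from the same table: "All secondary outcomes, as described in 5.2, will be further analyzed" by regression. Its general between-arm comparison of all other variables therefore does not reach mortality or duration either.

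Elsewhere, death ends participation (3.3, 4.4) and is a suspension criterion counted over all enrolled subjects (7.3).

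**The concern.** VFD falls when a patient stays on the ventilator and also when a patient dies. A VFD difference can therefore come from duration, from survival, or from both. Section 6.2 words the test as a test of duration, and no planned analysis shows which part produced the result.

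Two misreadings are possible. A gain in survival with unchanged ventilation times could be reported as shorter ventilation. A real shortening could be offset in the mean by more deaths and go unseen. A split of VFD chosen after the data are known, in an open-label trial, would be post hoc.

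**Working it through.** **The plan's own figures.** Section 6.3 takes as its basis "With a mean duration of mechanical ventilation of 7 days with a standard deviation of 2.9 days" and states "we expect the control group to have 21 ventilator free days". The sample sizes reproduce with a two-sided alpha of 0.05 and 80% power.

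- Normal approximation, n per arm = 2 × (1.960 + 0.842)² × 2.9² / d². For d = 3 this gives 14.7, rounded up to 15; for d = 2 it gives 33.0, rounded up to 34.
- Exact t-test: 15.7, so 16, and 33.99, so 34. These match the plan.
- Dropout: 34 / 0.9 = 37.8, so 38 per arm and 76 in total.

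The step from 7 ventilated days to 21 VFD is 28 − 7. It equates VFD with duration only if nobody dies.

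**Adding deaths.** Let m be 28-day mortality, μ the mean VFD in survivors and v the VFD credited to a patient who dies. Then mean VFD = (1 − m)μ + mv. From the plan: μ = 21 in controls, and a 2-day design effect, so 23 with a true reduction. Assumed, because the documents give neither: m, and v = 0 or 7. Section 6.1 does not say that deaths score 0, so v = 7 serves as a sensitivity case.

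*Identical durations, mortality differs.* The difference in mean VFD is (21 − v) × (difference in m).

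- Mortality difference that gives 2 days: 2/21 = 9.5 points (v = 0); 2/14 = 14.3 points (v = 7). With 38 per arm these are 0.095 × 38 = 3.6 and 0.143 × 38 = 5.4 deaths.
- 30% v 20% mortality: 21 × 0.10 = 2.1 days (v = 0); 14 × 0.10 = 1.4 days (v = 7).

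*True 2-day reduction in survivors, hidden by more deaths.* The intervention-arm mortality that makes the two means equal is m₁ = (23 − control mean) / (23 − v).

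| Control mortality | v = 0: m₁ (excess) | v = 7: m₁ (excess) |
|---|---|---|
| 10% | 4.1/23 = 17.8% (7.8 points) | 3.4/16 = 21.25% (11.25 points) |
| 20% | 6.2/23 = 27.0% (7.0 points) | 4.8/16 = 30.0% (10.0 points) |
| 30% | 8.3/23 = 36.1% (6.1 points) | 6.2/16 = 38.75% (8.75 points) |

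**Would the first case reach significance?** Take 30% v 20%, v = 0, survivor SD 2.9 and 38 per arm.

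- Control variance: 0.7 × (2.9² + 21²) − 14.7² = 98.5.
- Intervention variance: 0.8 × (2.9² + 21²) − 16.8² = 77.3.
- SE = √((98.5 + 77.3)/38) = 2.15 days; expected t = 2.1/2.15 = 0.98.
- In 20,000 simulated trials, about 16% were significant in favour of the intervention.
- Significance needs an observed difference of about 2 × 2.15 = 4.3 days, or 4.3/21 = roughly 20 mortality points.

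**The case against.** VFD is a legitimate composite, and its definition openly includes being alive. It contains duration, and deriving it requires each patient's vital status and ventilation history, so both components could be reported from data the trial must hold. Duration on its own would be no cleaner, because an early death shortens it. All of this stands. A reader might infer that the trial cannot answer its own objective, but the documents do not support that. The gap lies in wording and in what is prespecified.

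A reader might also infer that the plan will produce false significant claims about duration. The calculation does not show this. A 10-point mortality difference alone moves the estimate but usually leaves p above 0.05, and 6.2 calls such results inconclusive. In the masking case, part of the lost signal comes from the extra variance that deaths add, which is a sample-size matter and separate from this point.

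The 60% death criterion in 7.3 should not be read as expected mortality. It is a suspension ceiling over all enrolled subjects, and patients not expected to survive 48 hours are excluded.

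What remains is that reporting the components is possible but not required, and the sentence introducing the primary test names duration as what it determines.

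**Conclusion.** The point holds as a mismatch between the stated inference and the variable tested. As planned, a VFD difference cannot be attributed to duration rather than survival, because neither component is compared between arms.

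The sizes are illustrative. A mortality difference of about 9.5 to 14.3 points reproduces the 2-day design effect with no change in duration. An opposite difference of about 6 to 11 points removes a true 2-day reduction from the mean. Both rest on assumed mortality (10% to 30% in controls for the second), on deaths scored 0 or 7, and on the plan's 21 VFD in survivors. They describe bias in the estimate when it is read as duration, not a rate of wrong significant results.

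**What to change.** Keep VFD as the primary outcome.

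1. Reword 2.1 and the opening of the primary analysis in 6.2 so that the test and its conclusion are stated in terms of VFD.
2. Add to 5.2 and 6.2, by arm, 28-day mortality and ventilation duration/time to liberation. Show liberation as cumulative incidence to day 28 with death as a competing event, together with the cause-specific hazard of liberation. Add ventilator days in survivors, labelled descriptive because it conditions on an outcome after randomisation.
3. State that VFD alone will not be reported as an effect on duration, and that the components will be interpreted jointly.

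Joint reading is needed because the cumulative incidence of liberation also depends on mortality. If all survivors are liberated at identical times and all deaths occur on the ventilator, 30% v 20% mortality gives 70% v 80% liberated by day 28. Used alone as a condition for claiming a duration effect, that curve would support the claim wrongly.

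The cost is some wording and a few extra analyses, using death and ventilation data that VFD already requires. The downside for the sponsor is that a positive VFD result may not support a claim about duration.
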